#### 2.1.2. Descriptive Statistics in Summary Tables

- *Continuous variables* will be summarized using standard quantitative statistics: number of non-missing observations, mean, standard deviation, median, quartiles and range (minimum and maximum observed values). The number of missing observations will also be specified.
- *Categorical variables* will be summarized using classical frequency statistics: number of non-missing observations and percentages by categories. Percentages will be calculated on the number of non-missing observations, and will be displayed using one decimal. The number of missing observations will also be specified.

### 2.1.3. Inferential Analysis

Data will be compared between the two groups using bilateral tests at the type I error 5% level.

- *Continuous variables*: the appropriate test will be chosen depending on the data distribution.  
The normality of quantitative data will be tested using the Shapiro-Wilk test.
  - if the normality test pvalue is > 0.05, the data will be considered as normally distributed and the Student test will be used.
  - else, the data will be considered as not normally distributed and the Wilcoxon Rank Sum test will be used.
- *Categorical variables*: the appropriate test will be chosen depending on the expected cell frequencies:
  - If all expected cell frequencies are  $\geq 5$  then the Chi test will be used.
  - Otherwise, the Fisher's exact test will be used.

The 95% confidence interval in regurgitant volume mean difference from baseline to 12 months will be presented by treatment group. If assumptions of normality are violated, the 95% confidence interval will be calculated using the Hodges-Lehmann estimate and distribution-free confidence interval based on a Wilcoxon Rank Sum test.

Further supportive analyses will be conducted which characterize the longitudinal effect of treatment on regurgitant volume in a repeated measures regression model, using a mixed effects model approach. Fixed effects will be treatment group and time effect. Site effect will be a random effect. Interaction between treatment group and site will also be studied.

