## STATISTICAL ANALYSIS PLAN

REDUCE\_FMR - SAP\_V2  
2018\_08\_06\_CT

REDUCE FMR Trial

Page 14/22

- Significance level two-sided 0.05;
- Statistical power to detect design alternative hypothesis is 80%;
- Hypothesized mean regurgitant volume change (baseline to 12-month): Control group = -2.4ml; Treatment group = -12.4ml;
- Hypothesized standard deviation: Control group = 13ml; Treatment group = 13ml;
- 3:1 randomization allocation.

Under the assumptions outlined above, the estimated minimum required sample size is 76 subjects (57 Treatment, 19 Control).

A total of 120 subjects at up to 20 centers will be randomized, allowing for approximately 30% attrition (mortality, missing data and loss to follow-up) in the first 12 months of follow-up.

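### NT-BNP has no stated scale, time point or between-group estimate in the SAP; a log-scale, baseline-adjusted ratio with a 95% CI would give a more precise supportive result at almost no cost

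*SAP*

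**What the plan says.** SAP 2.1.3 compares the groups with two-sided 5% tests. For a continuous variable it runs Shapiro-Wilk first. If p exceeds 0.05 the Student test is used; "else, the data will be considered as not normally distributed and the Wilcoxon Rank Sum test will be used". No transformation is mentioned anywhere in the SAP.

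SAP 2.1.2 summarises continuous variables by mean, SD, median, quartiles and range, and the layout in SAP 4.1.1 adds a p-value. A between-group estimate with a confidence interval is specified only for regurgitant volume (SAP 2.1.3 and 2.4.2, Primary Endpoint). The repeated-measures model in SAP 2.1.3 also concerns regurgitant volume only. The analyses using baseline characteristics in SAP 2.4.6 cover the primary and secondary efficacy endpoints.

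NT-BNP falls under none of these. It is one name in the list of SAP 2.4.5 (Observational Data). The same list specifies change from baseline for diuretic dose but says nothing comparable for NT-BNP. Protocol 6.8 says observational data are reported with descriptive statistics as supportive evidence. Protocol 3.5.1, 3.7.3.1 and 3.8.1 to 3.8.3 collect NT-BNP at baseline, discharge, and 1, 6 and 12 months.

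**The concern.** A programmer working from the SAP alone would take NT-BNP as recorded, apply Shapiro-Wilk and, if the marker is skewed, report group summaries with a Wilcoxon p-value. That has two weaknesses.

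- If the marker responds proportionally, the largest absolute changes in either direction come mostly from patients with high baselines. Ranking absolute changes then mixes the treatment effect with baseline level. Ranking 12-month levels makes no use of each patient's own baseline.
- Neither route gives a reader the size of the between-group difference or its uncertainty.

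With a small Control group, a non-significant p-value without an interval is easily misread as no effect. NT-BNP is a laboratory value and depends less on effort than walk distance or questionnaires, so it is worth reporting well even in a supportive role.

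**Working it through.** **1. The plan's own figure.** SAP 2.2 gives no NT-BNP calculation; its sample size concerns regurgitant volume. It takes a two-sided 5% level, 80% power, three Treatment patients per Control patient, mean changes of −12.4 ml (Treatment) and −2.4 ml (Control), hence a difference of 10 ml, and a common SD of 13 ml. With noncentrality = 10 / (13 × √(1/n_T + 1/n_C)):

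- 54/18: 10 / 3.538 = 2.826, power 79.6%
- 57/19: 10 / 3.444 = 2.904, power 81.8%

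The smallest 3:1 design reaching 80% is therefore 76, which matches the plan: "the estimated minimum required sample size is 76 subjects (57 Treatment, 19 Control").

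**2. Evaluable numbers.** SAP 2.2 randomizes 120, "allowing for approximately 30% attrition (mortality, missing data and loss to follow-up) in the first 12 months of follow-up". 120 × 0.70 = 84, which at 3:1 is 63 Treatment and 21 Control. This borrows the plan's overall attrition allowance; missingness of NT-BNP itself is not given.

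**3. Assumed NT-BNP inputs (none is in the documents).** Log-normal at baseline and 12 months; log SD s of 0.8, 1.0 or 1.2; baseline-to-12-month log correlation r; Treatment/Control ratio 0.7 (a 30% reduction) or 0.8 (20%).

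**4. Closed-form check, s = 1.0, r = 0.7, ratio 0.7.** The effect is ln 0.7 = −0.357, and √(1/63 + 1/21) = 0.252.

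| Analysis on the log scale | SD | SE = SD × 0.252 | 0.357 / SE | Power |
|---|---|---|---|---|
| Change, t-test | s√(2 − 2r) = 0.775 | 0.195 | 1.83 | 44% |
| 12-month value, baseline as covariate | s√(1 − r²) = 0.714 | 0.180 | 1.98 | 50% |
| 12-month value alone, t-test | s = 1.0 | 0.252 | 1.42 | 29% |

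**5. Simulation, 63/21, ratio 0.7, 1,500 runs per row (power, %).** The standard error of a single entry is at most √(0.25/1500), or 1.3 points.

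| s | r | Wilcoxon, absolute change | t, log change | Log ANCOVA | Wilcoxon, 12-month level | t, log 12-month level |
|---|---|---|---|---|---|---|
| 0.8 | 0.6 | 41.0 | 51.3 | 58.4 | 39.5 | 40.9 |
| 0.8 | 0.8 | 63.5 | 79.1 | 83.3 | 40.1 | 41.3 |
| 1.0 | 0.7 | 33.5 | 43.5 | 48.9 | 27.0 | 27.7 |
| 1.2 | 0.6 | 20.5 | 25.4 | 31.1 | 21.8 | 23.3 |
| 1.2 | 0.8 | 33.7 | 44.6 | 47.6 | 18.1 | 19.4 |

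The row s = 1.0, r = 0.7 agrees with step 4.

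**6. Reading the results.**

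- Shapiro-Wilk rejects normality of absolute change in 97 to 100% of runs, so under these assumptions the rule does end in Wilcoxon.
- In these rows, Wilcoxon on absolute change loses between 25.4 − 20.5 = 4.9 and 79.1 − 63.5 = 15.6 points against log change. Extending r to 0.85 gives about 5 to 17 points for a 30% reduction. For a 20% reduction the loss is about 2 to 11 points.
- For 12-month levels, compare the last two columns: Wilcoxon loses 0.7 to 1.5 points here and about 0 to 3 over the whole grid. Ranks of single values do not change under a log transformation. The gap to log ANCOVA (for example 48.9 against 27.0) is the cost of leaving out baseline.

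**The case against.** The strongest reply is that NT-BNP is observational. It carries no power claim and no success criterion, and Protocol 6.8 calls for descriptive statistics, so lost power on it changes no trial conclusion. SAP 2.4.5 also lacks the explicit between-group comparison wording that SAP 2.4.4 (Safety) uses. A rank test on a skewed biomarker is valid and conventional. All of this stands and limits the weight of the point. It does not remove it: the general rule in SAP 2.1.3 exempts no variable, the table layout carries a p-value, and a descriptive report also needs a suitable scale.

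Four stronger readings are tempting, and the documents do not support them:

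- *That the plan chose the raw scale.* It is silent; raw scale is what the text yields by default.
- *That the loss is 10 to 20 points.* No such figure follows from the documents. It depends on assumed effect, SD and correlation, and under those used here the low end is about 2.
- *That the raw scale costs power on 12-month levels too.* It does not, as step 6 shows.
- *That no interpretable summary is produced.* Group medians and quartiles are planned. What is missing is a between-group estimate with an interval, and for NT-BNP it is missing on the Student route as well.

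Nor is NT-BNP the only objective support: the core-lab MR and left ventricular measures are read blind (Protocol 4.1.1 and 4.2.2.1).

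**Conclusion.** The point holds as a minor improvement. The SAP leaves the NT-BNP scale, time point and value-versus-change choice open, and plans no between-group estimate for it. If the marker is right-skewed, the normality rule leads to a rank test almost every time.

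On absolute change the cost against log change is about 5 to 17 points of power for a 30% reduction and about 2 to 11 for 20%. This rests on log-normality, 63/21 evaluable, log SD 0.8 to 1.2 and correlation 0.60 to 0.85. On levels, the cost comes from ignoring baseline. Even the better analysis often stays well below 80% power (48.9% at s = 1.0, r = 0.7), so the main gain is an effect size with an interval rather than a decisive test. The primary conclusion is not affected.

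**What to change.** In SAP 2.4.5, state that NT-BNP is analysed as log(NT-BNP) at each follow-up visit, with 12 months as the main time point and log baseline as covariate. Report the Treatment/Control ratio of geometric means with a 95% CI. Keep the Wilcoxon test as a check, and exempt NT-BNP from the Shapiro-Wilk rule in SAP 2.1.3.

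The cost is a few sentences and a small amount of extra programming, with no new data. The analysis relies on approximate log-normality, which the Wilcoxon check covers.

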3.3.1 Inclusion Criteria

The subject must meet **all** of the following criteria at the time of eligibility for randomization and the index procedure:

1. Diagnosis of dilated ischemic or non-ischemic cardiomyopathy
2. Functional Mitral Regurgitation:
2+ (Moderate), 3+ (Moderate/Severe), or 4+ (Severe)
3. NYHA II, III, or IV (refer to Appendix D for NYHA Classification)
4. Six Minute Walk distance of at least 150 meters and no farther than 450 meters
5. Subject meets anatomic screening criteria as determined by angiographic screening at the time of the index procedure to ensure that implant can be sized and placed in accordance with the Instructions for Use
6. Left Ventricular Ejection Fraction $\leq 50\%$
NOTE: Subjects with LVEF of 41- 50% can only be included if baseline NYHA is class III/IV **AND** MR grade is 3+/4+ (moderately-severe/severe)

7. LV end diastolic dimension (LVEDD) >55mm or LVEDD/BSA > 3.0cm/m²
8. Stable heart failure medication regimen for at least three (3) months (refer to Appendix G for definition of stable heart failure regimen)
9. Age ≥ 18 years old and ≤ 85 years old
10. The subject has read the informed consent, agrees to comply with the requirements, and has signed the informed consent to participate in the study
11. Female subjects of child-bearing potential must have a negative serum βHCG test

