### 2.4.5. Observational Data

The following analysis will be performed on the ITT population.

- Long-term safety (through 6 months (+14 days) and 12 months (+30 days) of follow-up):
  - Mortality;
  - Serious adverse events (SAE).
    - NYHA classification at each visit
    - Left ventricular hemodynamics:
      - Left ventricular end diastolic (LVEDD) and systolic (LVESD) dimensions;
      - Ejection fraction (LVEF);
      - Forward cardiac output (CO).
    - Functional Mitral Regurgitation (FMR) echocardiographic assessments
      - Vena Contracta (VC)
      - Effective regurgitant orifice area (EROA)
      - Mitral regurgitation jet area / Left atrial area (MRJA/LAA)
      - Mitral regurgitation grade
        - Left atrial size
        - Mitral annular diameter and area
        - Diuretic dose change from baseline to 6 months of follow-up and to 12 months of follow-up
        - Pulmonary artery systolic pressure (echo derived at rest & during exercise)
        - NT-BNP
        - Kansas City Cardiomyopathy Questionnaire (KCCQ)
        - Quality-of-Life Assessment (SF-12)

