### 4.2.3. Type 4: several variables by group and visit

			Group name			P-value
			Group 1 (N=XX)	Group 2 (N=XX)	Total (*) (N=XX)	
Visit 1	Var 1	N	XX	XX	0	
		1 st Modality	XX (XX.X%)	XX (XX.X%)	0 (0.0%)	0.XXX
		2 nd Modality	XX (XX.X%)	XX (XX.X%)	0 (0.0%)	(Test)
		Missing	XX	XX	0	
...	...	...	...	...	...	
...	Var n	N	XX	XX	0	
		1 st Modality	XX (XX.X%)	XX (XX.X%)	0 (0.0%)	0.XXX
		2 nd Modality	XX (XX.X%)	XX (XX.X%)	0 (0.0%)	(Test)
		Missing	XX	XX	0	
...	...	...	...	...	...	
Visit n	Var 1	N	XX	XX	0	
		1 st Modality	XX (XX.X%)	XX (XX.X%)	0 (0.0%)	0.XXX
		2 nd Modality	XX (XX.X%)	XX (XX.X%)	0 (0.0%)	(Test)
		Missing	XX	XX	0	
...	...	...	...	...	...	
...	Var n	N	XX	XX	0	
		1 st Modality	XX (XX.X%)	XX (XX.X%)	0 (0.0%)	0.XXX
		2 nd Modality	XX (XX.X%)	XX (XX.X%)	0 (0.0%)	(Test)
		Missing	XX	XX	0	

\* if needed

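### SAP 2.1.3 has no test for ordered categories, so by default NYHA class and MR grade go to chi-square or Fisher's exact test, which ignore order

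*SAP*

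**What the plan says.** SAP 2.1.3 opens with a general rule: "Data will be compared between the two groups using bilateral tests at the type I error 5% level". For categorical variables "the appropriate test will be chosen depending on the expected cell frequencies". If every expected count is at least 5 the test is chi-square; "Otherwise, the Fisher's exact test will be used". A rank test is already in the SAP, but only for continuous variables that fail the normality check: "the data will be considered as not normally distributed and the Wilcoxon Rank Sum test will be used". There is no branch for ordered categories.

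SAP 2.4.5 lists "NYHA classification at each visit" and "Mitral regurgitation grade" as observational data and names no test for either. Both are also in the baseline list (SAP 2.4.2, Baseline Patients' Characteristics), where variables are compared by Student, Wilcoxon, chi-square or Fisher as appropriate. The table shell in SAP 4.2.3, "Type 4: several variables by group and visit", has a p-value column.

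Both scales are ordered. Protocol Appendix D grades NYHA I to IV by increasing limitation, and inclusion criterion 2 (Protocol 3.3.1) ranks MR from 2+ moderate to 4+ severe. Protocol 6.8 says that observational data are reported descriptively.

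**The concern.** Chi-square and Fisher's exact test give the same p-value however the categories are arranged. A consistent move from class III to II counts no more than an erratic difference of the same size. The benefit that the trial expects is directional: Protocol 5.2.1 names less regurgitation and better function, and Protocol 1.3.6.2 reports NYHA in the earlier TITAN study as an improvement. For such a shift an order-blind test has less power, and it yields no effect estimate.

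The baseline class is collected, yet NYHA is listed visit by visit, with no change score or adjustment. The analysis using baseline characteristics in SAP 2.4.6 covers primary and secondary efficacy endpoints only, so it does not reach these two variables.

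At stake is the sensitivity of two supportive comparisons with a small Control arm.

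**Working it through.** **Step 1. The plan's own figure.** The only sample-size calculation in the documents is for regurgitant volume (Protocol 6.6, SAP 2.2): difference 10 ml, SD 13 ml, two-sided 0.05, 80% power, 3:1.

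- Normal approximation: Control n = (1 + 1/3) × 13² × (1.96 + 0.842)² / 10² = 17.7, so 18, total 72.
- Noncentral t at 54 + 18: noncentrality 10 / [13 × √(1/54 + 1/18)] = 2.83, power 79.6%.
- Noncentral t at 57 + 19: noncentrality 10 / [13 × √(1/57 + 1/19)] = 2.90, power 81.8%.

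The stated 76 (57 + 19) is reproduced. There is no such calculation for NYHA class or MR grade.

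**Step 2. Evaluable numbers.** 120 randomized 3:1 is 90 + 30. With 30% attrition: 90 × 0.7 = 63 and 30 × 0.7 = 21, total 84.

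**Step 3. Which branch of the rule applies.** The expected Control count in a class with n patients is n × 21/84 = n/4. Chi-square therefore needs at least 20 patients in every class. Four classes would need 80 of the 84 spread almost evenly; five would need 100, which is impossible at 84. In the simulations below with four or five categories and a one-directional effect, Fisher's exact test applied in at least 90% of tables.

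**Step 4. Power by simulation.** 3,000 trials per scenario, two-sided 0.05; Monte Carlo error about √(0.5 × 0.5/3000) = 0.9 points. The SAP rule was compared with a Wilcoxon rank-sum test whose variance is corrected for ties: (n₁n₂/12) × [(N + 1) − Σ(t³ − t)/(N(N − 1))], where t is the size of each tied group.

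Control distributions and odds ratios are assumptions. Under a common odds ratio (OR), treatment multiplies the odds of being in a given class or better by OR. Example: Control 10/40/45/5% has cumulative shares 10, 50 and 95%. With OR 3 the cumulative odds 0.111, 1 and 19 become 0.333, 3 and 57, that is 25, 75 and 98.3%. The Treatment classes are then about 25/50/23/2%.

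Results at 63 + 21, OR 3:

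| Assumed Control distribution | SAP rule | Wilcoxon | Gain (points) |
|---|---|---|---|
| NYHA, 10/40/45/5% | 52% | 65% | 13 |
| NYHA, 5/45/45/5% | 48% | 60% | 13 |
| NYHA, three classes, 15/45/40% | 51% | 62% | 11 |
| NYHA concentrated, 3/22/70/5% | 40% | 56% | 16 |
| MR grade, four grades, 20/35/30/15% | 55% | 66% | 11 |
| MR grade, five grades | 47% | 65% | 19 |

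Gains are taken before rounding. Over OR 2 to 4 the gain is 7 to 17 points at 57 + 19, 8 to 19 at 63 + 21, and 4 to 20 at 90 + 30. The smallest is three classes at 90 + 30 with OR 4 (88.6% against 92.8%). The largest is five grades at 90 + 30 with OR 2.5 (44.7% against 64.4%). Type I error is about 4 to 6% for both tests.

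**Step 5. Shifts that do not follow a common direction.** At 57 + 19, SAP rule against Wilcoxon: exchange between classes II and III only, 43% against 34%; top category emptied, 62% against 16%; spread to both tails, 46% against 2%. Here the SAP rule is the better test.

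**The case against.** Several points on the other side are sound.

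- Both variables are observational, no power is claimed for them, and Protocol 6.8 reports such data descriptively. MR severity is also measured by vena contracta, regurgitant orifice area and jet-area ratio, and patient status by KCCQ and NT-BNP; these quantitative measures already fall under Student or Wilcoxon. This limits the consequence. It does not settle the test, because SAP 2.1.3 calls for between-group tests of the data and SAP 2.4.5 makes no exception.
- The SAP does not assign chi-square or Fisher to these variables by name, and the shell in SAP 4.2.3 is generic. The assignment follows from the general rule. It is still the only rule given for categorical data.
- SAP 2.4.6 makes further use of MR grade, in responder and subgroup analyses, but gives no ordinal comparison.

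A reader might infer more than the documents support:

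- *That the loss is a known, fixed amount.* It is not, since neither document gives a distribution or an effect size for NYHA class or MR grade.
- *That the present rule has no advantage.* Step 5 shows that it has.
- *That the direction of effect would be hidden.* SAP 2.1.2 requires percentages by category and the SAP 4.2.3 shell displays them by group, so direction is visible.
- *That event severity (SAP 2.4.4) needs the same change.* Severity is recorded per event, one patient can have several events, and there is no baseline class. A rank test on events would break independence.

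**Conclusion.** The point holds as a gap in the SAP with a modest consequence. Under the only stated rule, NYHA class and MR grade would be compared by tests that ignore order and leave the baseline class unused. For a one-directional shift the cost is roughly 4 to 20 points of power over all scenarios, and about 8 to 19 points at 63 + 21.

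These figures rest on the assumed control distributions, on three to five categories, and on a common odds ratio of 2 to 4. The effect of ignoring the baseline class was not quantified. The primary test, the minimum of 76 and the 120 to be randomized are unaffected.

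**What to change.** In SAP 2.1.3 add a third class, ordinal variables, naming NYHA class and MR grade. Prespecify one method: the Wilcoxon rank-sum test with tie correction (equivalently the Cochran-Mantel-Haenszel row-mean-scores test with rank scores). Stratification by baseline class is optional, but the SAP should say which version is used. A proportional-odds common odds ratio with 95% CI, adjusted for baseline class, may be added as a supportive estimate if the model fits; with sparse classes and about 21 Controls it should not be the main method.

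Keep chi-square and Fisher for nominal and binary variables, and leave event severity out. Keep the category percentages by group and visit, so that a shift that is not one-directional can be seen. If no p-value is intended for these variables, in line with Protocol 6.8, SAP 2.4.5 should say so, and the choice of test no longer matters.

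The cost is a few lines of SAP text and one SAS procedure. The statistical price is lower power for shifts that are not one-directional.

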3.8.1 Follow-Up Schedule – One (1) Month

One (1) month (30 days \pm seven (7) days) after the index procedure, the study subject will return to the study site for follow-up evaluations. The evaluations at this visit will include:

- Physical examination
- Vital signs
- Echocardiogram (TTE)
Note: Study sites that have experience and necessary equipment may undertake exercise echocardiography in addition to the standard echocardiographic assessment required by the protocol.
- ECG (12-lead)
- Serum chemistries: sodium, potassium, chloride, glucose, BUN, creatinine, and NT-BNP
- Cardiac enzymes: cardiac troponin (cTn)
- CBC with differential, includes hemoglobin, hematocrit, platelets, and WBC
- Quality of Life questionnaires:

- KCCQ
- SF-12
- NYHA Classification assessment
- Functional assessment:
 - Six minute walk test
- Clinical assessments by the physician and other information to be evaluated and recorded as they occur including:
 - Concomitant medications
 - Adverse events

If the index procedure was discontinued before a CARILLON implant was attempted in a Treatment group subject, they are considered a Procedural Screen Failure and are followed through 1-month, then exited from the study.

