The clinical relevance of this magnitude of a difference is supported by other trials evaluating the clinical impact of functional mitral regurgitation. For example, Amigoni showed in the VALIANT trial database that a 1% increase in FMR was associated with an increased risk of heart failure hospitalization, and an increased risk of death or heart failure hospitalization.³² Extending the clinical significance to mortality, Grigioni showed in a group of patients with Q-wave MI that those patients with a regurgitant volume >30 ml demonstrated higher mortality than those regurgitant volume <30 ml (RR 1.13 per 10 ml RVol increase).³³ In CRT candidate patients with at least mild MR and an average LVEF $25 \pm 7\%$, Madaric showed that CRT decreased the regurgitant volume from 36 ± 19 ml to 25 ± 11 ml, but he also showed that even an increase in regurgitant volume from 25 ± 11 ml at rest to 29 ± 12 ml with exercise was statistically significant to $p < 0.001$.³⁴ Lastly, Bursi noted in their study of heart failure after myocardial infarction that patients with MR had worse outcomes, which exhibited a graded ‘dose-response’ relationship with the severity of MR, a pattern that supports causality.³⁵ These data taken together suggest that a small change in FMR (e.g., 1%) can be clinically significant, and the 10 ml difference between populations proposed in this study is similar to the magnitude of change seen in other trials, and is clinically relevant.

Data Analysis

The mean improvement in regurgitant volume for each treatment group, from baseline to twelve months, will be compared in a two-sided, two-sample t-test. The 95% confidence interval on the between-group difference will also be calculated and presented. If assumptions of normality are violated, the nonparametric Mann-Whitney test will be used to assess statistical significance, and the 95% confidence interval on the

difference between groups will be calculated using the Hodges-Lehmann estimate and distribution-free confidence interval based on a Wilcoxon Rank Sum test. The primary analysis will be conducted on the intent-to-treat population, and supportive analyses will be performed on the previously defined per-protocol and as-treated populations (reference Section 6.2: Study Analyses). Further supportive analyses will be conducted which characterize the longitudinal effect of treatment on regurgitant volume in a repeated measures regression model.

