### Parameter of Interest

The parameter of interest for each treatment group is the mean change from baseline in regurgitant volume, in milliliters, at 12 months.

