### 2.4.2. **Primary Endpoint**

The primary analysis will be performed on the Intent to treat (ITT) population.

The primary efficacy endpoint is to compare the change in regurgitant volume from baseline at 12 months between the treatment and control groups using a two-sided, two-sample t-test (or Wilcoxon Rank sum test as appropriate). The corresponding 95% confidence interval on the between-group difference will also be calculated and presented.

A sensitivity analysis of the primary efficacy endpoint analysis on the ITT population will be performed, using the last observation carried forward (LOCF) missing data imputation on the regurgitant volume at 12 months. The same comparison analysis as mentioned above for the primary efficacy endpoint will be performed.

Two other additional analyses will be performed on the primary efficacy endpoint on:

- As-treated population
- Per-protocol population

The same comparison analysis as for the primary efficacy endpoint mentioned above will be used

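### The supportive repeated-measures model of regurgitant volume has no treatment-by-time term, so it gives one visit-averaged effect, which in general is not the 12-month difference

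*SAP*

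**What the plan says.** Protocol 6.6 (Data Analysis) promises a supportive analysis to "characterize the longitudinal effect of treatment on regurgitant volume in a repeated measures regression model". It lists no model terms. SAP 2.1.3 repeats that purpose, adds that a mixed-effects approach will be used, and specifies: "Fixed effects will be treatment group and time effect. Site effect will be a random effect". It continues: "Interaction between treatment group and site will also be studied". No treatment-by-time term appears there or elsewhere in the SAP. The SAP also does not say whether the response is volume or change from baseline, whether baseline counts as a time point, or what the within-patient covariance is.

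The parameter of interest in SAP 2.2 is the "mean change from baseline in regurgitant volume, in milliliters, at 12 months". The primary analysis in SAP 2.4.2 is to "compare the change in regurgitant volume from baseline at 12 months between the treatment and control groups" by t-test or Wilcoxon test.

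**The concern.** The listed terms do not serve the stated purpose. A model with treatment and time as main effects fits a time course common to both arms and one constant gap between them. It can show the shared course but not how the treatment difference changes, and that change is what a longitudinal treatment effect means.

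No other listed analysis fills the gap. Protocol 3.8.1 to 3.8.3 require a resting echocardiogram at 1, 6 and 12 months, but the primary comparison uses 12 months only. The list under "Functional Mitral Regurgitation (FMR) echocardiographic assessments" in SAP 2.4.5 has vena contracta, EROA, jet-area ratio and MR grade, not regurgitant volume. The responder analysis in SAP 2.4.6 names no visit.

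The model also matters for missing data. SAP 2.2 allows about 30% attrition. SAP 2.1.1 drops patients without 12-month data from the primary analysis, and its only general imputation is LOCF. The repeated-measures model is the one listed analysis that could use dropouts' 1- and 6-month values towards a 12-month estimate without carrying them forward. As listed, it does not estimate that quantity. Its single result could look smaller or larger than the primary result only because earlier visits are averaged in.

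**Working it through.** **Plan's own figure.** The documents give none for this model. The primary sample size reproduces: for a two-sample t-test with difference 10 ml, SD 13 ml, two-sided 0.05 and 3:1 allocation, power is 0.796 at 54 + 18 and 0.8175 at 57 + 19. So 76 is the smallest 3:1 total with at least 80%. The point below does not touch it.

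**Inputs.** From SAP 2.2: SD 13 ml, a 12-month difference of -12.4 - (-2.4) = -10 ml, 3:1 allocation, 120 randomized, about 30% attrition. Assumed, because the documents are silent: the differences at 1 and 6 months, the within-patient correlation, and the dropout pattern. Complete data means 63:21 patients (0.70 × 120 = 84). With dropout, 90:30 patients are 95/85/70% observed at 1/6/12 months, the same in both arms and unrelated to outcome. These calculations therefore say nothing about bias in the completer t-test.

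**Formula.** With complete data and within-patient covariance V over the three visits, the expected treatment coefficient is w1·d1 + w6·d6 + w12·d12. Here d is the true difference at each visit, and the weights are the row sums of V⁻¹ divided by their total. With dropout, the same generalized least squares equations are summed over the dropout patterns.

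**Weights.** Exchangeable covariance with complete data gives 1/3 each. AR(1) in visit order gives weights in the ratio 1 : (1 - ρ) : 1, so ρ = 0.5 gives 1/2.5, 0.5/2.5, 1/2.5.

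| Covariance | Data | Weights at 1/6/12 months |
|---|---|---|
| Exchangeable | complete | 0.33/0.33/0.33 |
| Exchangeable, ρ 0.3 | dropout | 0.40/0.34/0.27 |
| Exchangeable, ρ 0.7 | dropout | 0.42/0.33/0.25 |
| AR(1), ρ 0.5 | complete | 0.40/0.20/0.40 |
| AR(1), ρ 0.7 | complete | 0.435/0.130/0.435 |
| AR(1), ρ 0.7 | dropout | 0.490/0.173/0.337 |

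Over all patterns tried, including AR(1) in calendar time, the 12-month visit carries a weight of 0.25 to 0.44.

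**Reported effect (ml).**

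| True difference at 1/6/12 months | Complete, exchangeable | Other patterns |
|---|---|---|
| -10/-10/-10 | -10.0 | -10.0 |
| -4/-7/-10 | (-4 - 7 - 10)/3 = -7.0 | -6.5 to -6.6 with dropout |
| -16/-13/-10 | (-16 - 13 - 10)/3 = -13.0 | -13.4 to -13.5 with dropout |
| -8/-12/-10 | (-8 - 12 - 10)/3 = -10.0 | -9.35 to -9.88 |
| -10/-5/0 | (-10 - 5 + 0)/3 = -5.0 | -5.74 with dropout, exchangeable ρ 0.5 |

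In rows two and three the gap from the 12-month value is 3.0 to 3.5 ml, 30 to 35% of the 10 ml design effect. In the last row the 12-month difference is zero and the model still reports about half of the 1-month effect.

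**Baseline as a fourth time point.** If raw volume were fitted with baseline among the responses, an expected difference of zero enters the average. With complete exchangeable data each visit has weight 0.25, so a constant -10 after the procedure is reported as 0.75 × (-10) = -7.5 ml. The other patterns give -5.8 to -7.0 ml.

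**With treatment-by-visit added.** The exact calculation with exchangeable ρ 0.5 returns the true difference at every visit in each trajectory it was run on (constant, -4/-7/-10, -14/-12/-10 and -10/-5/0), with and without dropout. A simulation used 120 patients, effects -4/-7/-10, a baseline covariate unrelated to change, REML with unstructured covariance, no site term, and 1,000 replicates at each of ρ 0.3/0.5/0.7. The mean 12-month differences were -10.0/-9.9/-9.9 (Monte Carlo SE 0.10), the mean SEs 3.20/3.14/3.02, and the 95% CI coverage 0.94/0.96/0.96. The averaged effect under the same dropout has SE 2.14/2.36/2.55. For comparison, the 12-month completers alone give 13 × √(1/63 + 1/21) = 3.28 ml.

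**The case against.** The best counter-argument is that the paragraph in SAP 2.1.3 is an outline. It also leaves out the response, the baseline handling and the covariance, and a model meant to describe a longitudinal treatment effect could be read as implying treatment-by-time. The intention may well have been there. But the SAP lists its fixed effects and names a different interaction, so a programmer following the text would leave treatment-by-time out.

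Second, the model is supportive and carries no alpha or decision rule. The primary test and its as-treated, per-protocol and LOCF versions are all 12-month comparisons. This stands, and it limits the consequence.

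Third, no harm can be shown from the documents. Every non-constant trajectory above is invented, and an implant designed to hold the annular reduction could have a roughly constant effect, in which case nothing is lost. This also stands: the figures show how the estimator behaves and do not forecast the trial. The baseline-as-response figures need a further assumption, since the endpoint elsewhere is change from baseline.

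Fourth, the simulation of the proposed model had no random site term, so its standard errors and coverage are for a slightly simpler model, and convergence with site included was not examined. This is a fair limit, and it is why the fix needs a stated fallback.

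**Conclusion.** The concern holds. With the terms as listed, the model cannot describe how the treatment difference changes over time, and its one treatment coefficient is in general not the 12-month parameter of SAP 2.2. The 12-month visit contributes roughly a quarter to under a half of the weight, depending on covariance and missing data. For assumed effects that change by 3 ml per visit, the reported number misses the 12-month difference by 3.0 to 3.5 ml, in either direction. It is correct if the effect is constant, and can be correct by chance otherwise. These sizes rest on assumed trajectories, correlations and dropout; the structural point rests only on the SAP text. It should be corrected, but it does not affect the primary test or the sample size.

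**What to change.** In SAP 2.1.3, specify:

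- **Response:** regurgitant volume at 1, 6 and 12 months, with baseline volume as a covariate. The treatment contrasts are then the same whether volume or change is fitted.
- **Fixed effects:** baseline volume, treatment, visit (categorical) and treatment-by-visit.
- **Covariance:** unstructured within patient, with a patient random intercept as the fallback if the model does not converge; random site intercept.
- **Reporting:** the 12-month difference with its 95% CI as the main result of this model, then the 1- and 6-month differences.

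Treatment-by-visit and the visit contrasts cure the defect. The remaining items settle choices the SAP leaves open. It would also help to label treatment-by-site as descriptive: 120 × 1/4 = 30 controls over up to 20 centers is 30/20 = 1.5 per center.

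The cost is one paragraph and standard SAS code, with no new data. The model gains 3 fixed-effect degrees of freedom (2 for treatment-by-visit, 1 for baseline). The unstructured matrix has 6 parameters and replaces at least one residual variance, so the net addition is at most 5. Under the assumed dropout the 12-month difference has an SE of 3.0 to 3.2 ml, against 2.1 to 2.6 ml for the averaged effect. The smaller figure belongs to a different quantity.
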